2. BACKGROUND	
2.1	
Background and rationale for research based on existing literature:
 
The rapid growth of the US population over age 80 that is expected to occur over the next 20 years will create enormous challenges to our health care system. Many of these elderly individuals will develop physical and cognitive disabilities that will make it difficult for them to live independently. Moreover, as a result of their medical needs, loss of income, and/or limited pensions, many will be poor and dependent on government support for their housing and health care needs. Currently, approximately 15% of seniors or 3.5 million people in the US live at or below the poverty level (Salkin). Many of these people are “dually-eligible” Medicare and Medicaid beneficiaries and live in Federal or State subsidized supportive housing facilities. Dually eligible beneficiaries are generally poor and frail with worse health status than other Medicare beneficiaries. They also tend to use more health care services, and account for a disproportionate share of Medicare spending, particularly for inpatient hospitalizations.^{1, 2} For example, dual eligible beneficiaries are 1.6 times more likely to be hospitalized than non dual eligible beneficiaries.[From Misha Segal, Policy Insight Brief, 9-2011]^{1, 3} Older adults living in public housing are twice as likely — 57.3 percent vs. 26.9 percent — to report fair or poor health compared to those with no public housing experience. (Ethnicity and Disease.)
 
Impact on scientific knowledge and clinical practice: Previous clinical trials have included highly selected populations of different ages, and interventions that have typically been limited to 12-24 weeks in duration and conducted in academic medical centers. Very few of these studies have involved poor, frail, and ethnically diverse elderly populations or employed long-term interventions based in community settings. Moreover, we are not aware of any studies that have directly evaluated impacts of Tai Chi on overall medical costs. The proposed study will determine whether Tai Chi is an effective and practical intervention to improve overall function and lower health care costs in an expensive, vulnerable population of seniors that is more representative of many US communities than those previously studied. If the results are favorable, our study will also provide the

necessary training and protocol manuals to replicate Tai Chi programs in senior housing facilities across the nation to help prevent, better manage, and overcome frailty among seniors.

Unlike several other practices that have beneficial effects on health and well-being, Tai Chi has several features that are particularly attractive in frail elderly populations and can improve compliance. First, previous studies, including our own, demonstrate that it is safe in patients with chronic disease.^{8,45,53,57} The exercises can be tailored to the capabilities of the participant, yet still have beneficial effects. In addition, many studies report higher adherence to Tai Chi than the comparison group or conventional exercise. This is important, particularly when dealing with populations of patients with chronic disease who have difficulty engaging in and sustaining conventional exercise. The relaxing effects, social interactions, self-efficacy, and continually reinforcing physical and psychological benefits of Tai Chi are intrinsic features that will likely promote long-term adherence.⁶⁵⁻⁶⁷

It is often challenging to enroll sedentary older adults in exercise programs, especially those who are economically disadvantaged or not well educated. Moreover, once recruited, it requires concerted effort to maximize participation and retention rates in the program. This is especially the case for our Tai Chi trial, which includes a year-long intervention, making it the longest Tai Chi intervention investigated in the context of a clinical trial in the United States. Therefore, the goal for the new amendment is to document effective strategies for increasing activity levels among older adults with a sedentary lifestyle, as a means to reducing disability and improving overall health.

2.2 Previous (non-clinical, pre-clinical or clinical) studies leading up to and supporting the proposed research:

Given the large and growing problem of supporting the health and health care needs of frail seniors living in subsidized housing, it is particularly important to identify interventions that can combat frailty, improve residents' functional abilities, and ultimately reduce their health care costs. Tai Chi is a particularly promising intervention that has enormous promise for ameliorating many of the conditions that lead to poor health and excessive health care utilization. In our previous studies, we have shown that it can be practiced successfully and without adverse effects by frail seniors living in supportive housing facilities and can result in significant improvements in balance, gait, and functional ability after only 12 weeks. However, it remains to be determined whether a longer period of Tai Chi exercise can improve the health of poor, frail seniors and reduce their health care utilization and cost.

Tai Chi is a mind-body exercise that originated in China, and that is growing in popularity in the West. It is based on slow intentional flowing movements, often coordinated with breathing and imagery, that aims to strengthen, relax and integrate the physical body and mind, and according to traditional Chinese medicine, enhance the natural flow of 'qi' (or life energy), improve health, and personal development.^{1,2} Surveys suggest that approximately 5 million Americans have practiced Tai Chi, and this number is increasing.^{3,4} Because of its reputed health benefits, apparent safety, low cost, and growing popularity, Tai Chi has become an increasingly recognized preventative and rehabilitative modality. Studies have shown that Tai Chi exercise can improve a number of medical conditions, including CHF,⁵⁻¹⁰ hypertension,¹¹⁻¹³ hyperlipidemia,^{11,14,15}

coronary artery disease,16-21 COPD,22-25 cardiorespiratory fitness,26-34 poor balance,35-40 reduced musculoskeletal strength and flexibility,26,31,32,35,41-44 Parkinson’s disease,45 rheumatological conditions,46-55 cognitive decline,56-62 and overall mood.63 Several Tai Chi review articles have been published.64

2.3 Describe why this research is important and how it will contribute to existing knowledge:

The proposed clinical trial will reinforce the concept that multi-system interventions are particularly beneficial in overcoming the chronic diseases and disabilities of older adults and will demonstrate the value of Tai Chi, as an effective, low cost, easily tolerated, universally available, yet currently underutilized intervention to improve the functional health of elderly people. The study will also help dispel the myth that aging is associated with an inevitable and irreversible functional decline, by demonstrating the ability of frail seniors to engage in and benefit from Tai Chi exercise.

Innovation: The proposed research is innovative, in our opinion, because: 1) it is based on a unique conceptual model derived from complex systems theory, 2) it engages a previously understudied, underserved, and expensive population in a unique academic-community partnership, and 3) it examines important economic and physiologic outcomes that have not been previously investigated, yet can lead to a better mechanistic understanding and downstream impact of our results.

Unlike previous studies, we will examine health care utilization and costs as outcomes of our Tai Chi intervention, in addition to traditional physiological and functional indicators of health. We will also examine novel measures of physiologic complexity of gait and balance developed to determine whether the effect of Tai Chi on overall functional ability is associated with improvements in the complex dynamics of these underlying control systems. Finally, we will determine features that will help us scale and sustain the program in the future – factors that influence compliance and ways to empower the community itself by training future Tai Chi trainers who work and live in the housing facilities we study.

Our results will add to the growing scientific literature to evaluate subjects’ experiences in clinical trials/programs to inform facilitators and barriers to adherence, engagement, and program satisfaction, and the processes that mediate health behavior change.

3. STUDY LOCATION

3.1 Study Site(s):

The study will emanate from HSL-IFAR, and the study will take place in multiple senior supportive housing sites in Boston, Brookline, Somerville and Lynn. The Housing Authorities of three communities have provided letters of support, included in this application.

3.2 Principal Investigator’s experience conducting research at study site(s), if outside of HSL facilities:

The Principal Investigator was the lead investigator for the MOBILIZE Boston Study, which recruited and followed longitudinally 765 volunteers over aged 70, who resided in the local communities, many of whom were residents of senior facilities in Brookline and elsewhere.

[name] has also worked collaboratively with the co-investigators in the past and each has significant expertise to contribute to the success of the current protocol. [name] has lead many community Tai Chi Studies over the past several decades and collaborated previously with [name] on a successful Tai Chi Intervention Study: The TEACH Study HSL IRB protocol 10-005

4 STUDY OBJECTIVES

Provide study objectives/aims/hypotheses:

Overall Aim: To conduct a cluster randomized controlled trial (RCT) of Tai Chi classes twice weekly (with interim video reinforcement), or health promotion educational classes and monthly social calls for 1 year in low-income elderly housing facilities in Brookline, Somerville, and Lynn Massachusetts.

Specific Aim 1: To determine the effects of the Tai Chi intervention on functional performance over a one-year period in poor, multiethnic, and functionally-limited elderly residents of low income housing facilities. To provide a similar level of attention and social engagement, the control group will participate in educational classes and monthly social calls. The primary functional outcome will be overall physical function as quantified by the Short Physical Performance Battery (SPPB). Secondary outcomes will include person-centered measures, including specific aspects of physical function, cognition, psychological well-being, falls, exercise self-efficacy, and satisfaction with the intervention. We hypothesize that participation in the Tai Chi classes will improve outcomes within each of these domains as compared to educational classes and monthly social calls.

Specific Aim 2: To determine the effects of the Tai Chi intervention on health care utilization and cost during the one-year periods during and following Tai Chi or educational classes in poor, multiethnic, elderly residents of subsidized housing facilities. The primary utilization outcomes will be emergency visits, hospitalizations, doctor visits, skilled nursing and nursing home admissions, and the total number of encounters. Cost outcomes will be total Medicare spending for hospital, emergency room, post-acute care, and physician or nurse office visits. We hypothesize that compared to the control intervention, the Tai Chi intervention will significantly reduce health care utilization and costs during the intervention period and one year afterward.

We will work within the ongoing Tai Chi clinical trial to address the following 2 aims:

Specific Aim 3: Determine demographic, social, psychological, and other factors that influence continuing participation in a year-long Tai Chi exercise intervention by residents of subsidized senior housing facilities in Boston through a series of focus groups for residents participating in and dropping out of the Tai Chi exercise program.

Specific Aim 4: Examine the predictors of long-term adherence to the Tai Chi exercise program by assessing the relationship between baseline demographic, health, functional, and psychosocial subject characteristics, which are being collected in the trial, with subsequent adherence to the intervention. We will quantify adherence by the number of Tai Chi sessions attended and will determine the characteristics of those most likely to complete the program.

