5 STUDY DESIGN								
5.1	
Study design (e.g., double-blind, placebo-controlled, parallel design): We will address our aims by conducting a cluster randomized controlled trial (RCT) of twice weekly group Tai Chi exercise sessions plus self-practiced video-directed supplemental sessions vs. an organized healthy aging educational program plus monthly social telephone calls, in low income senior housing facilities located within three diverse communities surrounding Boston. This is a pragmatic trial, rather than a comparative effectiveness or mechanistic study, which aims to determine the functional and health care utilization outcomes of Tai Chi compared to one's customary daily practices, while controlling for attention through the educational sessions. The added focus group sessions and withdrawal interviews are designed as a qualitative and descriptive study.
							
5.2	
Study duration (total): The study duration is expected to be 5 years in total.
 
A REVISED STUDY TIMELINE FOR COMPLETION OF FIELD ACTIVITIES AND DATA ANALYSIS IS ATTACHED.
							
5.3	
Duration of study for participants: Participants will be enrolled for about 26 months; The baseline assessment will occur within 4 weeks of the telephone screen; the study intervention of Tai Chi or health aging educational program sessions will last for 12 months; followed by a follow up assessment to occur within 4 weeks of completing the study intervention (a midpoint assessment will occur at 6 months from the start of the intervention). Participant visits will end at the follow up assessment, but Health Care Utilization data will be collected for the one year during the study intervention, and for one year following the completion of the intervention.
 
For each of the group (Tai Chi or health educational program), we will conduct three 30-45 min. focus groups, one within the first four months of the intervention, one within the second four months of the intervention, one within the last four months of the intervention.
 
For those who withdraw from the study, we will conduct individual interviews as close to the time of drop-out as possible.
							

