7 STUDY PROCEDURES

7.1 Study visits including procedures/tests involved (e.g., blood test, x-rays, questionnaires. If numerous study visits and procedures are involved, include a study procedure timeline):

The participant's Housing Site will be assigned by random, such as the flip of a coin, to participate in either a Tai Chi or Health and Wellness Activity study group. The participant will be asked to take part in whatever group his/her housing site has been assigned. Participants in the Tai Chi Activity group will be asked to attend for one hour twice a week for twelve months, or a total of 96 classes. Participants in the Health and Wellness Activity group will be asked to attend for one hour, once a month for a total of 12 classes.

Study Groups: The Tai Chi study group will be led by a certified Tai Chi instructor. It will consist of warm-up exercises, stretches, and Tai Chi movements developed for use with older adults. The participant will be asked to attend all of the classes in the assigned study group over the one year period. He/She may also be asked to watch and follow along with a Tai Chi instructional video in his/her apartment at his/her convenience one or two times each week for 15-30 minutes. If he/she does not have a video player, one will be provided

to use during your study enrollment. The video will consist of warm-ups, seated stretches, and simplified Tai Chi movements. The participant will be asked to keep a log of practice dates and times and bring this to class with them for review with the instructor, and will be regularly collected. The Health and Wellness Activity study group will also be led by a trained instructor. Activities will include lectures and discussions on healthcare topics of interest to older adults. All sessions will take place in a common room of the housing facility. The instructors will have access to water for participants and a phone in case of emergency. **PARTICIPANTS WHO ENROLLED IN WAVE 2, PAIR 3 WILL NOT TAKE PART IN EITHER OF THE STUDY INTERVENTIONS.**

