Assessments: Participants will be asked to complete an assessment described below on 3 separate occasions. The first assessment will occur before beginning the assigned activity group of either Tai Chi exercise sessions or Health and Wellness sessions, twice a week for one year. The second assessment will occur six months (+/- 3 weeks) after beginning the sessions and the third assessment will occur twelve months (+/- 3 weeks) after beginning the sessions. (Wave 2, participants from Housing site pairs 1 and 2, participation will end following the second assessment at six months. These participants will not be asked to complete a third assessment at twelve months. This is due to the recent decision by the NIA and DSMB to stop the study intervention at this time. Only these Wave 2 site pairs will have reached the point of the six month assessment at the time that the study intervention is stopped.) It will take about two hours to complete each of these three assessments. A trained research assistant will carry out the assessments which will take place in the participant's apartment or a private place at the housing facility.

1. **Health Interview** - At each of the three assessments, the participant will be asked questions about his/her health, medications, history of falls, whether he/she has had any hospitalizations or emergency room visits. Height, weight, blood pressure and heart rate will be measured. Participants will be asked questions about daily activities, mood, sleep, memory and balance.

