8 STATISTICAL PLAN

8.1 Statistical methods:

Analysis for each Aim: Specific Aim 1: To determine the effects of the Tai Chi intervention on functional performance over a one-year period in poor, multiethnic, elderly residents of subsidized housing facilities. The primary functional outcome will be the Short Physical Performance Battery (SPPB) score. We will also examine the effects of Tai Chi on self-reported physical and mental health, gait and balance, falls, executive function, social engagement, overall activity level, and other patient-centered outcomes.

The effect of the Tai Chi intervention on functional performance as measured by SPPB will be estimated from a shared-baseline linear mixed model with fixed effects for age, follow-up time, age x time interaction, and treatment x time interaction and random effects of community, site within community, participant within site, community x treatment, community x time, community x treatment x time, site x time, and participant x time interactions. The shared baseline across treatment groups reflects homogeneity of the population with respect to treatment prior to random assignment and adjusts for effects of baseline level in a manner equivalent to ANCOVA. The random effects acknowledge the expected correlations among sites within a community, among participants within a site, and among repeated longitudinal assessments of each participant. This approach also naturally accommodates unequal enrollment across sites and loss to follow-up, even potentially informative loss to follow-up, if well predicted by the observed data on participants prior to drop-out. All participants will be included in the primary analysis according to their treatment assignment, following the intention-to-treat principle. Primary inference will be based on a two-tailed test at alpha = 0.023 of the fixed treatment x time interaction estimating Tai Chi-dependent improvement in rates of change in SPPB. An additional alpha = 0.002 is reserved for one interim analysis. The total two-tailed alpha = 0.025 for testing SPPB preserves an overall type I error rate of 0.05 for the functional and utilization primary aims. In addition to intention-to-treat analyses, we will perform secondary per-protocol analyses, defining participants in a tai chi group as 'per-protocol' if they attended ≥50% of tai chi classes averaged over the year-long intervention.

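### The control is said to give similar attention and social engagement, but it schedules 12 class hours against 96 for Tai Chi

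*Combined protocol and SAP*

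**What the plan says.** Section 4, Specific Aim 1, gives the purpose of the control: "To provide a similar level of attention and social engagement, the control group will participate in educational classes and monthly social calls". Section 5.1 repeats the idea, saying that Tai Chi is compared with customary daily practices "while controlling for attention through the educational sessions". The same section describes the trial's character: "This is a pragmatic trial, rather than a comparative effectiveness or mechanistic study".

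Section 7.1 sets the schedule. Tai Chi participants are asked to attend one-hour classes twice weekly for twelve months, 96 in all. For the control, the "Health and Wellness Activity group will be asked to attend for one hour, once a month for a total of 12 classes". Later in Section 7.1, under Assessments, a looser sentence refers to "either Tai Chi exercise sessions or Health and Wellness sessions, twice a week for one year".

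Section 8.1 names the outcomes to be examined beside the SPPB. They include self-reported physical and mental health, and "gait and balance, falls, executive function, social engagement, overall activity level, and other patient-centered outcomes". Section 2.1 says of Tai Chi that "social interactions, self-efficacy, and continually reinforcing physical and psychological benefits of Tai Chi are intrinsic features".

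**The concern.** The plan attributes to the design a property that the schedule does not give it. A control that matches attention lets the analyst argue that a difference between arms is not simply the effect of meeting an instructor and a group of neighbors more often. A control that meets monthly, against twice weekly, does not support that argument.

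The conflict is sharpest for social engagement. The plan names social interaction as a working feature of Tai Chi, says the control is there to make social engagement similar, schedules far more group contact in one arm, and then examines social engagement as an outcome. A reader who accepts the attention claim would credit a difference in social engagement, psychological well-being or exercise self-efficacy to Tai Chi practice, when more group contact could produce it.

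**Working it through.** **Inputs**
- Tai Chi classes: 96, one hour each (Section 7.1).
- Control classes: 12, one hour each (Section 7.1).
- Monthly calls: 12 over the year. Sections 4 and 5.1 list social calls on the control side only. Section 7.1 describes monthly calls to participants without restricting them to one arm.
- Call length: not stated. Assumed here to be 10 to 60 minutes.
- Per-protocol threshold: Tai Chi participants count "if they attended ≥50% of tai chi classes averaged over the year-long intervention" (Section 8.1).

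**The plan's own figures**
- Tai Chi: 2 per week × 4 weeks × 12 months = 96 classes, so 96 hours. This reproduces the stated total.
- Control: 1 per month × 12 = 12 classes, so 12 hours. This also reproduces.
- Ratio: 96 / 12 = 8.0. Gap: 96 − 12 = 84 hours.

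**Adding the calls** (12 calls, total call hours = 12 × minutes / 60)

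| Assumed call length | Calls to controls only | Calls to both arms |
|---|---|---|
| 10 min (2 h) | 96 / 14 = 6.9 | 98 / 14 = 7.0 |
| 30 min (6 h) | 96 / 18 = 5.3 | 102 / 18 = 5.7 |
| 60 min (12 h) | 96 / 24 = 4.0 | 108 / 24 = 4.5 |

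Calls to controls only are the case most favorable to the plan. The call length that would equalize hours is 84 / 12 = 7 hours.

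**Allowing for poor Tai Chi attendance.** Take 50% attendance at Tai Chi and assume full attendance at the control classes:
- Class hours: 48 / 12 = 4.0.
- With 60-minute calls to controls only: 48 / 24 = 2.0.
- Call length for parity: (48 − 12) / 12 = 3 hours.
- Tai Chi attendance at which class hours are equal: 12 / 96 = 12.5%; with 60-minute calls to controls, 24 / 96 = 25%.

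**Counting contact common to both arms.** Section 7.1 has three assessments of about two hours (6 hours), and Section 5.3 offers three focus groups of 30 to 45 minutes (at most 2.25 hours). Adding 8.25 hours to each arm gives 104.25 / 20.25 = 5.1, or 104.25 / 32.25 = 3.2 if controls also receive 60-minute calls.

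**The loose sentence on frequency.** Read literally, the phrase under Assessments could give both arms two sessions a week. That cannot stand beside the control total of 12 classes. The sentence stating frequency and total for each arm is the specific one, so it governs.

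**The case against.** The strongest reply is that this is a pragmatic comparison of two programs. If social interaction and self-efficacy are intrinsic to Tai Chi, gains through group contact belong to the effect being estimated, and nothing is misattributed. No model, test or stopping rule in Section 8.1 depends on matched attention. Section 4 already states the contrast as Tai Chi classes against educational classes and monthly social calls, and Section 7.1 gives the unequal schedule openly. This stands as a defense of the light control. It does not defend the statement that the control makes attention similar, because a reader given that statement will interpret the program contrast more narrowly than the design allows.

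Some further points have force:
- Social engagement is missing from Specific Aim 1's own list of secondary outcomes and appears only in Section 8.1. The assessments in Section 7.1 describe no specific measure of it.
- Specific Aim 1 words the similarity as a purpose, not as a finding.
- Pairing 50% Tai Chi attendance with full control attendance is illustrative; the documents give no attendance data.
- Contact is wider than classes and calls. Counting the shared contact lowers the ratio, but not to parity.

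These limit the weight of the point. They do not remove the contradiction.

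**Conclusion.** The concern holds: the attention statements are wrong as written. Scheduled class time is 8 to 1. With calls to controls only, at an assumed 10 to 60 minutes, it is 6.9 to 1 down to 4 to 1. Hours become equal only with calls of about 7 hours, or with Tai Chi attendance of 12.5% (25% if controls also get hour-long calls).

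The consequence is for interpretation, and its weight is modest. It bears mainly on social engagement, psychological well-being, self-efficacy and other self-reported outcomes. It is weaker for the performance-based SPPB and for utilization taken from claims. Extra contact would tend to favor Tai Chi, so it does not readily explain the SPPB futility result reported in Section 8.1. The conclusion takes the per-arm schedule in Section 7.1 as governing and treats call length as an assumption.

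**What to change.** 1. In Sections 4 and 5.1, delete or qualify the statements that the control equalizes or controls for attention.
2. State the effect as that of the whole Tai Chi program, including its greater group contact, against monthly education plus calls.
3. Report attended contact hours by arm. Section 11.1 already lists class attendance as a data source. Say which arm receives the monthly social calls and about how long they last.
4. When reporting social engagement, mood, self-efficacy and other self-reported outcomes, add that contact time differed between arms and could account for a difference.
5. In Section 7.1 under Assessments, correct the session frequency so that it agrees with the per-arm schedule.

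The cost is wording plus one descriptive summary. The sample size and the primary analysis do not change. The trial gives up the claim that attention was controlled.
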